8.2.1.1. Tumor Imaging During Screening

Initial tumor imaging should be performed within 28 days before the first dose of study treatment. The site study team must review prestudy images to confirm that the participant has measurable disease per RECIST v1.1. For the purpose of response assessment, a biopsied lesion may only be selected as a target lesion if postbiopsy imaging confirms that it still qualifies as a RECIST defined measurable lesion, unless there are other lesions that qualify the participant for RECIST assessment. Further, lesions used for the purpose of response assessment must either a) not reside in a field that has been subjected to prior radiotherapy or b) have demonstrated clear

evidence of radiographic progression since the completion of prior radiotherapy and prior to study enrollment..

An MRI scan or CT of the brain will be performed at screening if there is a previous history of CNS metastasis or there are signs or symptoms suggesting that the participant has disease involvement in the CNS.

Scans performed as part of routine clinical management are acceptable for use as the screening scan if they are of diagnostic quality and performed within 28 days before the first dose of study treatment.

8.2.1.2. Tumor Imaging During the Study

The first imaging assessment should be performed 8 weeks (± 7 days) after the first dose of study treatment and then Q8W (± 7 days) for 12 months and then Q12W (± 7 days) thereafter until PD is determined. Imaging assessments may be done more frequently if clinically indicated. Imaging should not be delayed for delays in cycle starts.

Repeated brain imaging during the treatment phase will be performed only if the screening brain imaging was positive or as clinically indicated. If indicated, brain imaging should occur at same time (± 2 weeks) as disease assessment scans. Whenever feasible, contrast-enhanced brain MRI is preferred to CT.

Per RECIST v1.1, response should be confirmed by a repeat radiographic assessment not less than 4 weeks from the date that the response was first documented. The scan for confirmation of response may be performed at the earliest 4 weeks after the first indication of response or at the next scheduled scan, whichever is clinically indicated.

Imaging should continue to be performed until documented PD, the start of new anticancer treatment, withdrawal of consent, death, or the end of the study, whichever occurs first. A central imaging vendor will not be used in this study.

8.2.2. Health Economics

Not applicable; health economics parameters are not evaluated in this study.

8.3. Safety Assessments

See Section 6.5 for guidelines regarding the management of relevant laboratory or other safety assessment abnormalities.

8.3.1. Adverse Events

Adverse events will be monitored from the time the participant signs the ICF until at least 90 days after the last dose of study treatment regardless of the start of a new anticancer therapy. Adverse events for randomized participants that begin or worsen after informed consent should be recorded on the Adverse Events Form in the eCRF regardless of the assumption of a causal relationship with the study treatment. Conditions that were already present at the time of informed consent should be recorded on the Medical History Form in the eCRF. Adverse events (including laboratory abnormalities that constitute AEs) should be described using a diagnosis whenever possible rather than by individual underlying signs and symptoms.

Adverse events will be reported by the participant (or, when appropriate, by a caregiver, surrogate). The investigator and any qualified designees are responsible for detecting, documenting, and recording events that meet the definition of an AE or SAE and remain responsible for following-up on AEs that are serious, considered related to the study treatment/procedures, or that caused the participant to discontinue the study treatment. Care will be taken not to introduce bias when detecting AEs and/or SAEs. Open-ended and nonleading verbal questioning of the participant, such as "How are you feeling?" is the preferred method to inquire about AE occurrences. Adverse events may also be detected when they are volunteered by the participant during the screening process or between visits or through physical examinations, laboratory tests, or other assessments. The definition, reporting, and recording requirements for AEs are described in Section 9.

All SAEs will be reported to the sponsor or designee within 24 hours. The investigator will submit any updated SAE data to the sponsor within 24 hours of it being available.

After the initial AE/SAE report, the investigator is required to proactively follow each participant at subsequent visits/contacts. All SAEs will be followed until resolution, stabilization, the event is otherwise explained, or the participant is lost to follow-up (as defined in Section 7.3).

8.3.2. Physical Examinations

Physical examinations must be performed by a medically qualified individual, such as a licensed physician, physician's assistant, or an advanced registered nurse practitioner, as local law permits. Abnormalities identified after the first dose of study treatment constitute an AE if they are considered clinically meaningful, induce clinical signs or symptoms, require concomitant therapy, or require changes in study treatment. Investigators should pay special attention to clinical signs related to previous serious illnesses.

At the screening visit, a comprehensive physical examination should be conducted. The comprehensive physical examination will include height and body weight, and assessment(s) of the following organ or body systems: skin; head, eyes, ears, nose, and throat; thyroid; lungs; cardiovascular system; abdomen; extremities; and lymph nodes; as well as a brief neurological examination.

During the study, participants will be assessed by the investigator or medically qualified designee per institutional SoC. These assessments should be an evaluation as indicated by participant symptoms, AEs, or other findings and documented on the AE eCRF. Body weight will also be assessed on Day 1 of each cycle.

8.3.3. Vital Signs

Vital sign measurements (to be taken before blood collection for laboratory tests), include blood pressure, pulse, respiratory rate, and body temperature at each required assessment timepoint. Vital signs will be monitored before and/or after study drug infusions as per Table 3 and Section 6.1. Blood pressure and pulse will be taken with the participant in the recumbent, semirecumbent, or sitting position after 5 minutes of rest. Abnormal vital sign results identified after the first dose of study treatment constitute an AE if they are considered clinically meaningful, induce clinical signs or symptoms, require concomitant therapy, or require changes in study treatment.

8.3.4. Electrocardiograms

Triplicate 12-lead ECGs will be obtained as outlined in [Table 3](#) at screening, Day 1 of Cycles 1 through 5, on Day 1 of every fourth cycle beginning at Cycle 9, at EOT, and as clinically indicated. All 12-lead ECGs will be performed with the participant in a recumbent or semirecumbent position after 5 minutes of rest.

All 12-lead ECGs will be performed using an ECG machine that automatically calculates the heart rate and measures PR, QRS, QT, and QTc intervals. Triplicate ECGs require 3 individual ECG tracings obtained as closely as possible in succession and up to approximately 2 minutes apart. The 12-lead ECGs will be interpreted by the investigator at the site to be used for immediate participant management. Additional 12-lead ECGs may be performed as clinically indicated to manage participant safety. The decision to include or exclude a participant or discontinue a participant from the study treatment based on an ECG flagged as "Abnormal, Clinically Significant" is the responsibility of the investigator, in consultation with the medical monitor, as appropriate. Clinically notable abnormalities that are considered clinically significant in the judgment of the investigator are to be reported as AEs. In the event that a single QTc is > 460 milliseconds at screening, the participant may enroll if the average QTc for the 3 ECGs is ≤ 460 milliseconds or with approval from the medical monitor. For participants with an intraventricular conduction delay (QRS interval > 120 milliseconds) at screening, the JTc interval may be used in place of the QTc with medical monitor approval. In addition, the JTc interval should be used for all subsequent assessments.

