5. STUDY POPULATION

Deviations from eligibility criteria are not allowed because they can potentially jeopardize the scientific integrity of the study, regulatory acceptability, and/or participant safety. Therefore, adherence to the criteria as specified in the Protocol is essential. Prospective approval of Protocol deviations to recruitment and enrollment criteria, also known as Protocol waivers or exemptions, are not permitted.

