 18. History of organ transplant, including allogeneic stem cell transplantation.
 19. Receiving probiotics as of the first dose of study treatment.
 20. History or presence of an abnormal ECG that, in the investigator's opinion, is clinically meaningful. Screening QTc interval > 460 milliseconds is excluded (corrected by Fridericia or Bazett formula). In the event that a single QTc is > 460 milliseconds, the participant may enroll if the average QTc for the 3 ECGs is ≤ 460 milliseconds.
 21. Has had a significant cardiac event within 6 months before the first dose of study treatment, including New York Heart Association Class III/IV, acute myocardial infarction (including severe/unstable angina), cardiomyopathy, coronary/peripheral artery bypass graft, symptomatic congestive heart failure, critical conduction delay, cerebrovascular accident or transient ischemic attack, or pulmonary embolism.

Note: Medically-controlled arrhythmia is permitted.

Note: Recovery from uncontrolled or Grade ≥ 3 hypertension to ≤ Grade 1 is required.

22. Has received a live vaccine within 30 days of planned start of study treatment.

Note: Examples of live vaccines include but are not limited to the following: measles, mumps, rubella, chicken pox/zoster, yellow fever, rabies, Bacillus Calmette–Guérin, and typhoid vaccine. Seasonal influenza vaccines for injection are generally killed virus

vaccines and are allowed; however, intranasal influenza vaccines are live-attenuated vaccines and are not allowed.

23. Known hypersensitivity to another monoclonal antibody that cannot be controlled with standard measures (eg, antihistamines and corticosteroids).
24. Known allergy or hypersensitivity to any component of either retifanlimab, INCAGN02385, or INCAGN02390 study drug formulation (including excipients and additives).
25. Women who are pregnant or breastfeeding.
26. Any condition that would, in the investigator's judgment, interfere with full participation in the study, including administration of study treatment and attending required study visits; pose a significant risk to the participant; or interfere with interpretation of study data.
27. The following participants are excluded in France: vulnerable populations according to article L.1121-6 of the French Public Health Code and adults under legal protection, or who are unable to express their consent per article L.1121-8 of the French Public Health Code.

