8.5. Electrocardiograms

Twelve-lead ECGs including heart rate, PR, QRS, QT, QTcF, and QTcB intervals will be obtained for each participant during the study. Values at each scheduled timepoint, change, and percentage change from baseline will be summarized for each ECG parameter. Baseline will be determined as the average of all nonmissing values before the first administration of study drug.

Normal ranges for ECG values are defined in [Table 10](#). Electrocardiogram values will also be considered abnormal if the absolute percentage change from baseline is more than 25% (30% for QRS interval). Participants exhibiting ECG abnormalities will be listed with study visit and assigned treatment group. Abnormal values for participants with alert ECG values, defined as both the absolute value and the percentage change from baseline being outside normal ranges, will be identified and listed. Outliers of QT, QTcB, and QTcF values, defined as absolute values > 500 milliseconds, > 460 milliseconds, or change from baseline > 30 milliseconds, will be summarized.

Table 10: Normal Ranges for Electrocardiogram Intervals

Parameter	High Threshold	Low Threshold
PR	≤ 220 ms	≥ 75 ms
QRS	≤ 120 ms	≥ 50 ms
QT	≤ 500 ms	≥ 300 ms
QTcF, QTcB	≤ 460 ms	≥ 295 ms
Heart rate	> 100 bpm	< 50 bpm

QTcB = Bazett's correction; QTcF = Fridericia's correction.

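### Protocol 8.3.4 allows JTc in place of QTc at screening without a formula or limit, and exclusion 20, which has no JTc provision, excludes some of the same participants

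*Protocol*

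**What the plan says.** **Protocol 8.3.4 (Electrocardiograms).** After a single screening QTc above 460 ms, "the participant may enroll if the average QTc for the 3 ECGs is ≤ 460 milliseconds or with approval from the medical monitor". The next sentence concerns anyone whose screening QRS is above 120 ms. In that group, "the JTc interval may be used in place of the QTc with medical monitor approval". The section then makes JTc the interval to use at all later assessments. It attaches no number to JTc and gives no formula. The ECG machine it calls for reports heart rate, PR, QRS, QT and QTc, so a site would have to derive JTc itself.

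**Protocol 5.2, exclusion criterion 20.** "Screening QTc interval > 460 milliseconds is excluded", by Fridericia or Bazett correction. The only relief is a mean of the three ECGs at or below 460 ms. Neither JTc nor medical monitor approval is mentioned. The same criterion has a non-numeric arm: "History or presence of an abnormal ECG that, in the investigator's opinion, is clinically meaningful".

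**Protocol 5 (Study Population).** "Prospective approval of Protocol deviations to recruitment and enrollment criteria, also known as Protocol waivers or exemptions, are not permitted".

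**SAP 8.5.** The ECG parameters are heart rate, PR, QRS, QT, QTcF and QTcB; JTc is not among them. Outliers of QT, QTcB and QTcF are "defined as absolute values > 500 milliseconds, > 460 milliseconds, or change from baseline > 30 milliseconds".

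**The concern.** A screening limit works only if the measurement and the number belong to the same scale. JTc leaves out the QRS, so it is shorter than QTc, and by most in the participants with a wide QRS to whom the sentence applies. The protocol lets JTc take the place of QTc directly after a sentence whose only number is 460 ms. It does not say whether that number, another number or no number then applies.

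The list of exclusion criteria has no matching provision. A site that follows 5.2 and a site that follows 8.3.4 can reach opposite decisions on the same ECG. At stake are consistent application of a cardiac safety criterion across sites and the status of anyone enrolled through the JTc route, who could later be classed as an eligibility violation. The missing formula and limit also carry into treatment, because 8.3.4 continues JTc at later assessments.

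**Working it through.** The documents state no JTc figure, so there is none to reproduce. The check sets the two rules side by side and then shows what each open reading implies.

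**Inputs from the documents**
- QTc entry limit: 460 ms (Protocol 5.2, criterion 20; Protocol 8.3.4).
- QRS that opens the JTc route: above 120 ms (Protocol 8.3.4).
- Outlier line for QT and QTc: above 500 ms (SAP 8.5).

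**Assumption not in the documents.** JTc = QTc − QRS. As a variant, JT = QT − QRS is itself rate-corrected, with heart rates of 50 to 100 bpm taken as the range.

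**Step 1. One participant under both sections.** Take QRS 130 ms and a mean QTc of 500 ms, so JTc = 500 − 130 = 370 ms.

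| Rule | Result |
|---|---|
| Criterion 20 (5.2) | 500 > 460: excluded; the three-ECG mean gives no relief, and there is no JTc provision |
| 8.3.4, if 460 ms is read across to JTc | 370 ≤ 460: may enrol, with monitor approval |
| 8.3.4, if 460 ms is not read across | no stated limit: left to the monitor's judgment |

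On either reading of 8.3.4, a participant whom 5.2 excludes may be enrollable.

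**Step 2. QTc that would match JTc = 460 ms, if 460 ms were read across.** QTc = 460 + QRS.
- QRS 121 ms: 460 + 121 = 581 ms
- QRS 130 ms: 460 + 130 = 590 ms
- QRS 150 ms: 460 + 150 = 610 ms

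Conversely, QTc ≤ 460 ms with QRS > 120 ms means JTc < 460 − 120 = 340 ms. Reading 460 ms across would therefore loosen the limit by the width of the QRS, more than 120 ms.

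**Step 3. Sensitivity to the missing formula.** If JT itself is corrected, QTc = 460 + QRS/RR^(1/2) for Bazett or 460 + QRS/RR^(1/3) for Fridericia, where RR = 60/heart rate in seconds. At QRS 120 ms:

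| Heart rate | RR (s) | Bazett | Fridericia |
|---|---|---|---|
| 50 bpm | 1.2 | 460 + 109.5 = 569.5 ms | 460 + 112.9 = 572.9 ms |
| 60 bpm | 1.0 | 580.0 ms | 580.0 ms |
| 100 bpm | 0.6 | 460 + 154.9 = 614.9 ms | 460 + 142.3 = 602.3 ms |

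The range is about 570 to 615 ms, so the choice of formula alone moves the answer by some 45 ms at a fixed QRS.

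**The case against.** **Criterion 20 still bars entry.** This is the strongest reply. Section 5.2 excludes any mean screening QTc above 460 ms, and Section 5 disallows waivers. That stands, and it means the QTc limit is contradicted, not switched off. It does not remove the problem. If criterion 20 governs, the screening JTc sentence admits nobody whom the QTc rule would not admit anyway. If 8.3.4 governs as a built-in provision, criterion 20 is incomplete. The protocol does not say which section prevails.

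**Other safeguards apply.** The JTc route needs medical monitor approval. Criterion 20 excludes a clinically meaningful ECG abnormality on the investigator's judgment, and criteria 21 and 26 cover critical conduction delay within 6 months and significant risk to the participant. All of this stands: 460 ms is the only numeric QTc limit, not the only ECG control. None of these safeguards supplies a JTc formula or limit.

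**8.3.4 already lets the monitor approve above 460 ms.** True, and it weakens any claim about size, since within 8.3.4 the number is not firm even for QTc. But criterion 20 has no such approval clause either, so this is a second disagreement between the same two passages.

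**JTc is a reasonable measure when the QRS is wide.** That is not disputed. The question is which number goes with it. With the SAP Table 10 normal QRS range of 50 to 120 ms, a QTc of 460 ms corresponds to a JTc of 460 − 120 = 340 to 460 − 50 = 410 ms. A JTc of 460 ms would be 50 to 120 ms longer than that, so reading 460 ms across would do more than adjust for conduction delay.

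**A stronger inference.** A reader might infer that the plan lets a participant with a wide QRS enter with a QTc of about 580 ms or more. The documents do not support that. They neither attach 460 ms to JTc nor define JTc; approval and the ECG-abnormality exclusion still apply; and criterion 20 says the opposite. Nor should the SAP's 500 ms line be taken as an entry limit, because it is a descriptive summary category. The ECGs and troponin tests added because of data from other LAG-3 agents are described as cardiac safety monitoring, and no QT signal is named.

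**Conclusion.** The point holds as an inconsistency on a safety-related eligibility criterion. Section 8.3.4 permits JTc in place of QTc without a formula or limit. Criterion 20 does not provide for JTc, and the protocol forbids waivers. The same participant can be excluded under one section and possibly enrollable under the other. This conclusion needs only the text.

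The size is conditional. The figures above 580 ms rest on two assumptions that the documents do not make: that 460 ms carries over to JTc, and that JTc = QTc − QRS. Under the variant definition the range is about 570 to 615 ms at QRS 120 ms. The documents do not say how many participants have a QRS above 120 ms at screening; the number is probably small. No effect on the primary PFS analysis is claimed. The change is worth making because it is cheap and removes a conflict on who may enter, but it is not critical to the trial.

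**What to change.** Reconcile Protocol 8.3.4 with exclusion criterion 20 so that both say the same thing about whether JTc may determine eligibility and, if it may, by what formula and against what limit. The difference between the two passages on medical monitor approval can be settled in the same edit. The decision belongs to the sponsor and its cardiology adviser; no value or rule is proposed here.

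The cost is about two sentences, one in each section, and possibly a few more screen failures, depending on what is decided.

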8.3.5. Eastern Cooperative Oncology Group Performance Status

The ECOG performance status will be assessed at the timepoints indicated in [Table 3](#) according to the criteria in [Table 13](#).

Table 13: Eastern Cooperative Oncology Group Performance Status

Grade	ECOG Performance Status
0	Fully active, able to carry on all predisease performance without restriction
1	Restricted in physically strenuous activity but ambulatory and able to carry out work of a light or sedentary nature (eg, light house work, office work)
2	Ambulatory and capable of all self-care but unable to carry out any work activities; up and about more than 50% of waking hours
3	Capable of only limited self-care; confined to bed or chair more than 50% of waking hours
4	Completely disabled; cannot carry on any self-care; totally confined to bed or chair
5	Dead

Source: [Oken et al 1982](#).

8.3.6. Laboratory Assessments

See [Table 14](#) for the list of clinical laboratory tests to be performed and [Table 4](#) for the timing and frequency. A certified laboratory local to the investigative site will perform all clinical laboratory assessments for safety (ie, blood chemistries, hematology assessments, coagulation tests, lipid panel, thyroid function, serology, pregnancy testing, and urinalysis). The investigative site will enter the laboratory results and laboratory normal ranges into the eCRF. Additional

testing may be required by the sponsor based on emerging safety data. Additional tests may also be performed if clinically indicated.

Clinically significant abnormal laboratory findings are those that are not associated with the underlying disease, unless judged by the investigator to be more severe than expected for the participant's condition. All laboratory tests with values considered clinically significantly abnormal during participation in the study or within 30 days after the last dose of study treatment should be repeated until the values return to normal or baseline or are no longer considered clinically significant by the investigator or medical monitor.

Screening laboratory assessments must be performed within 28 days before Cycle 1 Day 1. If screening chemistry and hematology analyses are performed within 7 days before initial administration of study treatment, they do not need to be repeated on Cycle 1 Day 1.

Laboratory sample collection on Cycle 1 Day 1 must be performed before study treatment administration. After Cycle 1, predose laboratory procedures can be conducted up to 72 hours before study treatment administration (within the 3-day study window), and results should be reviewed by the investigator or qualified designee and found to be acceptable before a new cycle of treatment is initiated.

Table 14: Required Laboratory Analytes

Blood Chemistries	Hematology	Urinalysis	Serology
Albumin Alkaline phosphatase ALT AST Amylase Bicarbonate, CO ₂ or HCO ₃ (if clinically indicated) Blood urea nitrogen or urea Calcium Chloride Creatinine Glucose Lactate dehydrogenase Lipase Phosphate Potassium Sodium Total bilirubin (also direct bilirubin, if total bilirubin is elevated above ULN) Total protein Troponin (TnT or TnI) level (per local standard) Uric acid	Complete blood count, including: 
 Hemoglobin Hematocrit Platelet count Red blood cell count WBC count Differential count, including: 
 Basophils Eosinophils Lymphocytes Monocytes Neutrophils Absolute values must be provided for: 
 WBC differential laboratory results 	pH and specific gravity Bilirubin Glucose Ketones Leukocytes Nitrite Occult blood Protein Urobilinogen Microscopic examination (if blood or protein is abnormal)	HBV screening and management (required): 
 HbsAg Total anti-HBc Anti-HBs HBV-DNA When applicable per investigator discretion: 
 IgM anti-HBc HCV screening: 
 HCV antibody HCV-RNA quantitative HIV antibodies only if mandated by local health authorities or local regulations. HIV management (if HIV-positive): 
 HIV viral load CD4+ cell count
	Lipids	Coagulation	Pregnancy Testing
	Total cholesterol Triglycerides LDL HDL	PT PTT or aPTT INR	Human chorionic gonadotropin (serum or urine)
		Thyroid Function TSH T4 fT4 FT3/T3 as clinically indicated	

Note: Additional laboratory analytes used for management of AEs/SAEs, ruling out a diagnosis, or participant management are permissible during the study.

Note: Alternative tests to the above may be conducted instead or in addition if they are the SoC in a particular region.

Note: Additional tests may be required, as agreed upon by the investigator and sponsor, based on emerging safety data, or based on regional geographical differences, or depending on the extent of COVID-19 pandemic. Relevant test results will be documented in eCRFs.

